10.6.12.3 Nursing/Breast-feeding

It is not known whether the study drugs and/or their metabolites are excreted in human milk. Because of the potential harm to the infant, mothers should discontinue nursing/breast-feeding during treatment with study all study drugs and for at least 4 months after completing therapy.

11.0 POTENTIAL TOXICITIES, DOSE MODIFICATION AND MANAGEMENT OF TOXICITIES

11.1 Potential Toxicities

11.1.1 CB-839

The most frequent AEs considered possibly or probably related to CB-839 monotherapy dosed on the BID schedule on the Phase 1 CX-839-001 study were fatigue, gastrointestinal events (nausea, vomiting, and constipation), photophobia, anemia, dyspnea, and elevations in liver function tests (see [Table 9.5-1](#)). These have been primarily Grade 1/2 AEs that have been manageable and reversible with minimal dose modifications or delays.

The most frequent Grade 3/4 AEs considered possibly or probably related to monotherapy CB-839 were LFT elevations (see [Table 9.5-1](#)).

11.1.2 Cabozantinib

The safety and tolerability profile of cabozantinib is well defined and outlined in the Cabometyx (cabozantinib) US Prescribing Information (or local equivalent). A summary is provided below:

Adverse events most frequently observed with cabozantinib ($\geq 25\%$ of patients) are diarrhea, fatigue, nausea, decreased appetite, palmar-plantar erythrodysesthesia syndrome, hypertension, vomiting, weight decreased, and constipation. The majority of these AEs have been of mild to moderate severity (CTCAE Grade 1-2). Grade 3-4 adverse reactions and laboratory abnormalities which occurred in $\geq 5\%$ of patients were hypertension, diarrhea, fatigue, palmar-plantar erythrodysesthesia syndrome, hyponatremia, hypophosphatemia, hypomagnesemia, lymphocytes decreased, anemia, hypokalemia, and GGT increased. Cabozantinib has been

associated with a low incidence of severe and potentially lethal AEs, including hemorrhage, GI perforations and fistulas, thrombotic events, hypertension and hypertensive crisis, diarrhea, palmar-plantar erythrodysesthesia syndrome, reversible posterior leukoencephalopathy syndrome, and embryo-fetal toxicity (see Warnings and Precautions in the Cabometyx (cabozantinib) US Prescribing Information [or local equivalent]).

11.1.3 Dose Modification Guidelines

11.1.3.1 Study Drug Dose Levels

The possible dose levels for CB-839/placebo and cabozantinib are provided in [Table 11.1-1](#) and [Table 11.1-2](#).

Table 11.1-1: Dose Levels for CB-839/Placebo

Dose Level	CB-839/Placebo Dose
Starting dose	800 mg BID (1600 mg daily)
First dose reduction	600 mg BID (1200 mg daily)
Second dose reduction	400 mg BID (800 mg daily)
Third dose reduction	Discontinue

Table 11.1-2: Dose Levels for Cabozantinib

Dose Level	Cabozantinib Dose
Starting dose	60 mg oral QD
First dose reduction	40 mg oral QD
Second dose reduction	20 mg oral QD
Third dose reduction	Discontinue

11.1.3.2 Study Drug Dose Modifications

Dose modifications may be considered for each study drug independently. Modifications, including dose interruption and resumption, dose reduction, dose re-escalation, and permanent

discontinuation of each study drug will be based on the investigator's discretion, with the following exceptions:

- The dose of each study drug cannot exceed the starting dose
- Interruptions of study drug are allowed for up to 6 weeks (continuous) without Medical Monitor consultation, although it is strongly recommended that interruptions in dosing are as brief as possible. Resumption of study drug in a patient with a dose interruption lasting > 6 weeks requires discussion with and approval by the Medical Monitor (see [Section 11.2](#))
- Both study drugs should be interrupted for Grade ≥ 3 elevated ALT, AST, or bilirubin and restarted at reduced doses after ALT, AST, and bilirubin levels resolve to Grade ≤ 1 or baseline
- Suspected drug-induced liver injury should be reported to the Medical Monitor; both study drugs should be interrupted and then resumed only after discussion with and approval by the Medical Monitor (see [Section 11.1.4.2](#))
- Dose re-escalation is not allowed for a dose reduction triggered by study drug-related myelosuppression or Grade 4 life-threatening AEs affecting major organs
- Permanently discontinue cabozantinib for any of the following:
 - Development of unmanageable fistula or GI perforation
 - Severe hemorrhage
 - Arterial thromboembolic event (e.g., myocardial infarction, cerebral infarction)
 - Hypertensive crisis or severe hypertension despite optimal medical management
 - Nephrotic syndrome
 - Reversible posterior leukoencephalopathy syndrome

Additional guidelines for treatment modifications and AE management are provided below in [Table 11.1-3](#) and in [Section 11.1.4](#). These guidelines are based on the Cabometyx (cabozantinib) US Prescribing Information and the clinical experience with CB-839, cabozantinib, and the combination to date. Because cabozantinib prescribing information may change over time, the most up-to-date Cabometyx (cabozantinib) US Prescribing Information (or local equivalent) should also be consulted and followed.

These guidelines are intended primarily for toxicities that investigators assess as *related to study treatment* (CB-839/placebo or cabozantinib) and that are not easily managed with routine supportive care. In general, all AEs should be managed with supportive care at the earliest signs. Dose interruptions of cabozantinib should be as brief as possible.

Unless otherwise specified (see exceptions under Study Drug Dose Modifications above), dose modifications and AE management guidelines presented in this protocol are only recommendations and are not intended to supersede the clinical judgment of the treating physician.

Table 11.1-3: Treatment Modifications Guidelines for Treatment-Related AEs

Toxicity Grade (CTCAE v4)	CB-839/Placebo	Cabozantinib
Grade 1-2	If manageable and tolerable, continue current dose with supportive care.	
	If not tolerable, interrupt dosing and resume at same dose level upon recovery. If Grade 2 toxicity recurs, interrupt and restart at next lower dose.	
Grade 3 (except non-clinically relevant laboratory abnormalities)	Interrupt dosing and resume at the same dose level or next lower dose level upon recovery.	Interrupt dosing, unless toxicity can be easily managed with a dose reduction, and resume at the next lower dose level upon recovery.
Grade 4 (except non-clinically relevant laboratory abnormalities)	Interrupt dosing immediately. Discontinue study drug unless the patient is deriving clear clinical benefit, as determined by the investigator and agreed by the Medical Monitor, and the toxicity can be managed with a dose reduction and optimal medical care.	

11.1.4 Cabozantinib Warnings, Precautions, and Guidelines for Management of Potential Adverse Events

Below are guidelines for the treatment and/or prevention of certain treatment-emergent AEs of interest that have been associated with, or have a theoretical possibility of occurring with, cabozantinib treatment.

11.1.4.1 Gastrointestinal Disorders

The most common GI AEs reported in clinical studies with cabozantinib are diarrhea, oral pain, dyspepsia, stomatitis, and dysphagia.

Diarrhea

Patients should be instructed to notify their study doctor or site staff immediately at the first signs of poorly formed or loose stool or an increased frequency of bowel movements.

Administration of antidiarrheal/ antimotility agents is recommended at the first sign of diarrhea as initial management. Some patients may require concomitant treatment with more than one antidiarrheal agent. When therapy with antidiarrheal agents does not control the diarrhea to tolerable levels, consider temporary dose interruption or reduction per [Table 11.1-3](#). When the diarrhea is controlled, retreatment with study treatment may be acceptable per investigator decision.

In addition, general supportive measures should be implemented including continuous oral hydration, correction of fluid and electrolyte abnormalities, small frequent meals, and stopping lactose-containing products, high fat meals, and alcohol.

Nausea and Vomiting

Antiemetic agents are recommended as clinically appropriate at the first sign of nausea and vomiting or as prophylaxis to prevent emesis, along with supportive care according to clinical practice guidelines. The 5-HT₃ receptor antagonists are recommended over chronic use of NK-1 receptor antagonists and dexamethasone (NK-1 receptor antagonists can induce or inhibit CYP3A4, and glucocorticoids induce CYP3A4 and thus could lower cabozantinib exposure). Caution is also recommended with the use of nabilone, which is a weak inhibitor of CYP3A4.

Stomatitis and Mucositis

Preventive measures may include a comprehensive dental examination to identify any potential complications before study treatment is initiated. Removal of local factors should be instituted as indicated, such as modification of ill-fitting dentures and appropriate care of gingivitis. During treatment with cabozantinib good oral hygiene and standard local treatments such as nontraumatic cleansing and oral rinses (e.g., with a weak solution of salt and baking soda) should be maintained. The oral cavity should be rinsed and wiped after meals, and dentures should be cleaned and brushed often to remove plaque. Local treatment should be instituted at the earliest onset of symptoms. Obtain bacterial/viral culture if oral infection is suspected and treat infection as indicated by local guidelines. When stomatitis interferes with adequate nutrition and local therapy is not adequately effective, dose reduction or temporary withholding of cabozantinib should be considered.

11.1.4.2 Hepatobiliary Disorders

Elevations of ALT, AST, and bilirubin have been observed during treatment with cabozantinib. It is recommended that patients with elevation of ALT, AST, and/or bilirubin have more frequent laboratory monitoring of these parameters. If possible, hepatotoxic concomitant medications should be discontinued in patients who develop increased values of ALT, AST, or bilirubin.

Patients on this study may enter with increased ALT/AST serum levels up to $3 \times \text{ULN}$. Dose reductions of study treatment should be considered in any patient who develops drug-related Grade 2 elevated ALT, AST, or bilirubin lasting longer than 1 week. A patient who develops Grade ≥ 3 elevated ALT, AST, or bilirubin should have study treatment held and restarted at a reduced dose (see [Table 11.1-3](#)) after ALT, AST, and bilirubin levels resolve to at least Grade ≤ 1 or baseline. In patients with recurrence of drug-related Grade ≥ 3 elevated ALT, AST, or bilirubin at the lowest dose level, study treatment should be discontinued. In patients who develop ALT/AST elevations $> 3 \times \text{ULN}$ in combination with a bilirubin elevation $> 2 \times \text{ULN}$ without reasonable other explanation, drug-induced liver injury should be suspected and study treatment interrupted. Reinstitution of study treatment after recovery of ALT, AST, and bilirubin to Grade 1 or baseline level must be discussed and approved with the Sponsor.

11.1.4.3 Hematological Disorders

Hematological toxicities (i.e., neutropenia and thrombocytopenia) and associated complications have been observed after administration of cabozantinib and may be managed with dose interruptions and/or dose reductions. Use of granulocyte colony-stimulating factor support for neutrophil recovery is allowed per investigator discretion and in accordance with accepted guidelines after the first incidence of clinically relevant cytopenia.

Complete blood counts with differentials and platelets should be performed regularly. Patients with hematologic toxicities may require additional or more frequent laboratory tests according to institutional guidelines.

Febrile neutropenia or evidence of infection associated with neutropenia must be assessed immediately and treated appropriately and in a timely manner according to institutional guidelines. Dose reductions or dose interruptions for anemia are not mandated but can be applied as clinically indicated. Supportive care such as red blood cell transfusions may be managed according to institutional guidelines.

11.1.4.4 Fatigue, Anorexia, and Weight Loss

Fatigue has been reported during treatment with cabozantinib. Common causes of fatigue such as anemia, deconditioning, emotional distress (depression and/or anxiety), nutrition, sleep disturbance, and hypothyroidism should be ruled out and/or these causes treated according to standard of care. Individual non-pharmacological and/or pharmacologic interventions directed to the contributing and treatable factors should be given. Pharmacological management with psychostimulants such as methylphenidate should be considered after disease specific morbidities have been excluded. Note: Chronic use of modafinil should be avoided because of its potential to reduce cabozantinib exposure.

Dose reduction of study treatment should be considered when general or pharmacological measures have not been successful in reducing symptoms. Dose interruption may be considered for Grade ≥ 3 fatigue despite optimal management, at the investigator's discretion.

Anorexia and weight loss should be managed according to local standard of care including nutritional support. Pharmacologic therapy such as megestrol acetate should be considered for appetite enhancement. Should these interventions prove ineffective, dose hold and reductions may be considered for Grade ≥ 3 anorexia or weight loss. If anorexia and/or weight loss do not recur after a dose reduction, dose of cabozantinib may be re-escalated to the previous dose.

11.1.4.5 Skin Disorders

Palmar-plantar erythrodysesthesia syndrome

Palmar-plantar erythrodysesthesia (PPE) syndrome (also known as hand-foot syndrome), skin rash (including blisters, erythematous rash, macular rash, skin exfoliation, dermatitis acneiform, and papular rash), pruritus, dry skin, and erythema have been reported in cabozantinib-treated patients. All patients on study should be advised on prophylactic skin care. This includes the use of hypoallergenic moisturizing creams, ointment for dry skin, and sunscreen with sun protection factor ≥ 30 , avoidance of exposure of hands and feet to hot water, protection of pressure-sensitive areas of hands and feet, and use of thick cotton gloves and socks to prevent injury and to keep the palms and soles dry. Patients with skin disorders should be carefully monitored for signs of infection (e.g., abscess, cellulitis, or impetigo).

Early signs of hand-foot syndrome could be tingling, numbness, and slight redness or mild hyperkeratosis. Early manifestations include painful, symmetrical red and swollen areas on the palms and soles. The lateral sides of the fingers or peri-ungual zones may also be affected. Adequate interventions are required to prevent worsening of skin symptoms such as blisters, desquamations, ulcerations, or necrosis of affected areas. Aggressive management of symptoms is recommended, including early dermatology referral. Treatment guidelines for PPE related to study treatment are presented in [Table 11.1-4](#).

In the case of study treatment-related skin changes (e.g., rash, hand-foot syndrome), the investigator may request that additional assessments be conducted with the patient's consent. These assessments may include digital photographs of the skin changes and/or a biopsy of the affected skin and may be repeated until the skin changes resolve.

Table 11.1-4: Management of Treatment-emergent PPE Syndrome

CTCAE v.4.0 Grade	Action To Be Taken
1	Cabozantinib treatment may be continued at the current dose if PPE is clinically insignificant and tolerable. Otherwise, cabozantinib should be reduced to the next lower dose level. Start urea 20% cream twice daily and clobetasol 0.05% cream once daily. Reassess at least weekly; if PPE worsens at any time or does not improve after 2 weeks, proceed to the intervention guidelines for Grade 2.
2	Cabozantinib treatment may be continued if PPE is tolerated. Cabozantinib should be dose reduced or interrupted if PPE is intolerable. Continue urea 20% cream twice daily and clobetasol 0.05% cream once daily and add analgesics (e.g., NSAIDs/GABA agonists) for pain control if needed. Reassess at least weekly; if PPE does not improve within 2 weeks or worsens or affects self-care, proceed to the intervention guidelines for Grade 3.
3	Interrupt cabozantinib treatment until severity decreases to Grade 1 or 0. Continue treatment of skin reaction with clobetasol 0.05% cream twice daily and analgesics. Resume cabozantinib at reduced dose if PPE recovers to Grade 1 or 0. Discontinue patient from study if intolerable PPE recurs after dose reduction or does not improve within 6 weeks.

CTCAE, Common Terminology Criteria for Adverse Events; GABA, gamma-amino butyric acid; NSAID, non-steroidal anti-inflammatory drug; PPE, palmar-plantar erythrodysesthesia.

Wound Healing and Surgery

VEGF inhibitors can cause wound healing complications and wound dehiscence which may occur even long after a wound has been considered healed. Therefore, surgical and traumatic wounds must have completely healed prior to starting cabozantinib treatment and be monitored for wound dehiscence or wound infection while the patient is being treated with cabozantinib.

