10.3 Study Treatment Procedures

For the complete list of schedules of procedures, please refer to the Schedule of Assessments in [Attachment 1](#).

While the patient is receiving study treatment, the patient's clinical status should be evaluated at each clinic visit to confirm that the patient is suitable for continuing study treatment and to make timely decisions regarding the interruption or restarting of study treatment.

Assessments are based on 28-day cycles. *Radiographic evaluation of tumor burden and QoL questionnaires will be performed as scheduled relative to the date of Cycle 1 Day 1 (C1D1) regardless of study treatment holds or delays.* Additional assessments may occur, as clinically indicated, during unscheduled visits.

After randomization, clinic visits for safety evaluations will occur Day 1 of every cycle (approximately every 4 weeks) for the first 12 cycles. Starting with Cycle 13, safety evaluations will occur every 3 cycles (approximately every 12 weeks). More frequent safety evaluations may be performed if clinically indicated. The final scheduled safety assessment will occur at the End of Treatment Visit. If the study treatment is held due to AEs, Investigators should perform additional safety assessments as clinically indicated.

Radiographic evaluation of tumor burden (e.g., diagnostic computed tomography [CT] scan with intravenous contrast or MRI) will occur during Screening (within 28 days prior to randomization), every 8 weeks after C1D1 for the first 12 cycles, every 12 weeks beginning with Cycle 13, and at the End of Treatment Visit. Radiographic assessments may occur more frequently as clinically indicated.

Quality of life questionnaires will be completed before study drug dosing on C1D1, every 4 weeks after C1D1 for the first 12 cycles, every 12 weeks beginning with Cycle 13, and at the End of Treatment Visit.

Patients who hold or discontinue only one of the study drugs (either CB-839/placebo or cabozantinib) for any reason such as, but not limited to, an AE or surgery, should continue the other study drug on study and continue to have scheduled study visits and procedures per protocol.

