radiographic studies at the next scheduled time, and delay determination of progression until the findings indicating radiographic progression are unequivocal.

- Patients who discontinue study treatment for reasons other than progressive disease by RECIST v1.1 or death will continue to be followed by radiographic tumor imaging until documentation of radiographic progressive disease per RECIST v.1.1, death, initiation of a new anticancer therapy, or withdrawal of consent.
- If study treatment continues beyond Investigator-assessed progression because the patient is receiving clinical benefit from continued treatment (see [Section 11.3](#)), radiographic tumor assessments will also continue until the patient discontinues study treatment. This practice has the benefit of providing radiographic studies for IRC review beyond Investigator-assessed progression, which may be helpful in the case of discordance between the Investigator and the IRC regarding the date of progression.

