11.2 Resumption of Study Treatment

After withholding a study drug for an adverse event suspected to be related to that study drug, it is generally recommended that administration of the study drug is resumed when the AE has returned to \leq Grade 1 or baseline; however, investigator discretion may be used to determine if resolution to Grade 1 is necessary prior to reintroducing study treatment. If CB-839/placebo is restarted after permanent discontinuation of cabozantinib, it is also recommended that CB-839/placebo be permanently discontinued for a \geq Grade 3 recurrence of the AE that resulted in cabozantinib discontinuation. Following a dose reduction of CB-839/placebo or cabozantinib, re-escalation to the previous dose may be allowed at the discretion of the investigator.

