11.3 Discontinuation of Treatment

The reasons a patient may discontinue study treatment include, but are not limited to, the following:

- Patient no longer experiences clinical benefit as determined by the investigator. If study treatment is withdrawn for this reason, the date this decision is to be recorded and every effort should be made to continue safety evaluations, tumor assessments, and collection of subsequent anticancer treatment information and follow-up information for survival.
- Unacceptable side effects the investigator feels may be due to study treatment.
- Investigator feels it is not in the best interest of the patient to continue on study.

- Patient participation in another clinical study using an investigational agent or investigational medical device
- Necessity for treatment with other systemic anticancer therapy (non-protocol defined)
- Necessity for withholding study drug for greater than 6 weeks (continuous) for study-treatment related AEs
- Refusal of sexually active fertile patients to use medically accepted highly effective methods of contraception
- Female patient becomes pregnant
- Patient request to discontinue study treatment (with or without concurrent withdrawal of consent)
- Significant patient noncompliance with the protocol schedule in the opinion of the investigator or the Sponsor
- Sponsor request

The Sponsor should be notified of all patient withdrawals (from study treatment or from the study) as soon as possible. The reason for treatment discontinuation, the date of the decision to discontinue treatment, and the date of the last known dose of study treatment will be recorded in the end-of-treatment eCRFs. For patients who withdraw or are withdrawn from study treatment, the investigator should perform all End of Treatment Visit and follow up procedures as indicated in the schedule of study assessments ([Attachment 1](#)), and continue protocol-specified evaluations and procedures unless consent to participate in the study is also withdrawn. All patients will be followed until death, unless consent to do so is specifically withdrawn by the patient or until a decision by the Sponsor is made to stop collection of these data. *Note that in order to maximize detection of progression events for the study primary endpoint patients who discontinue study treatment for reasons other than progressive disease or death will continue to be followed by radiographic tumor imaging as described in [Section 10.6.9](#).*

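### The Grade 3 hand-foot syndrome (PPE) row of Protocol Table 11.1-4 takes the patient off the study, where the follow-up rules keep imaging and survival follow-up going

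*Protocol*

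**What the plan says.** Table 11.1-4 in Protocol 11.1.4.5 gives one row per PPE grade. All three rows act on cabozantinib, and none mentions CB-839/placebo. The Grade 3 row interrupts cabozantinib, resumes it at a lower dose on recovery, and ends: "Discontinue patient from study if intolerable PPE recurs after dose reduction or does not improve within 6 weeks".

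Other parts of the protocol bear on the same patient:

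- Protocol 10.6.9: "Patients who discontinue study treatment for reasons other than progressive disease by RECIST v1.1 or death will continue to be followed by radiographic tumor imaging". Imaging ends only at progression, death, new anticancer treatment or withdrawn consent. Protocol 7.0 and footnote 16 of Attachment 1 repeat the rule, and SAP section 4 carries it over.
- Protocol 11.3: for anyone coming off treatment, sites are to "continue protocol-specified evaluations and procedures unless consent to participate in the study is also withdrawn". Survival follow-up runs to death unless the patient withdraws consent for it or the sponsor stops collecting the data. The section treats leaving study treatment and leaving the study as two different events.
- Protocol 10.3: patients who hold or stop just one drug, including for an adverse event, "should continue the other study drug on study and continue to have scheduled study visits and procedures per protocol".
- Protocol 11.1.3.2: "Dose modifications may be considered for each study drug independently", and, later in the same section, "dose modifications and AE management guidelines presented in this protocol are only recommendations".

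**The concern.** The row makes a cabozantinib decision at every step and then, at the last one, ends the patient's participation in the study. A site managing severe hand-foot syndrome will have this table open, and nothing in the cell points to the follow-up rules.

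Two things are at stake. First, a patient taken off the study without progression has no further scans. IRC-assessed PFS is then censored at the last evaluable assessment, for a reason tied to toxicity and possibly to prognosis. Second, the same patient may drop out of survival follow-up, which feeds the key secondary endpoint. Both losses are avoidable, because the protocol elsewhere intends to keep collecting these data. Protocol 11.3 says that imaging continues after such stops in order to capture as many progression events as possible for the primary endpoint.

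**Working it through.** The question is mainly one of text, so the possible readings are set against the rest of the protocol first.

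**Reading A, literal: the patient leaves the study.** Scans and survival contacts stop. This conflicts directly with 7.0, 10.6.9 and 11.3, and with footnote 16 on imaging. PPE is not among the conditions that end imaging or survival follow-up. The six-week limit in the row does not help: 11.3 lists "Necessity for withholding study drug for greater than 6 weeks (continuous) for study-treatment related AEs" as a reason to stop study treatment, not to leave the study.

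**Reading B: the patient stops all study treatment but stays in follow-up.** This contradicts nothing outright. The 10.3 rule covers patients who stop only one drug. The sentence on independent modification in 11.1.3.2 is permissive. Protocol 11.2 is conditional ("If CB-839/placebo is restarted after permanent discontinuation of cabozantinib") and requires no restart. Still, the fit is poor: the row gives no reason to stop CB-839/placebo, and 10.3 directs sites to continue the other drug when one is stopped for an adverse event.

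**Reading C: the patient permanently stops cabozantinib.** This agrees with the rest of the row and with every section above.

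**Neighbouring rules.** Hypertensive crisis (Table 11.1-5), nephrotic syndrome (Table 11.1-6), arterial events (11.1.4.7), severe bleeding (11.1.4.11) and perforation or fistula (11.1.4.12) stop cabozantinib only. Recurrent severe liver elevations at the lowest dose (11.1.4.2) and life-threatening PE or DVT (11.1.4.7) stop study treatment. None of these removes the patient from the study. For clinically relevant bleeding on anticoagulation, 11.1.4.7 raises further participation only as a matter to discuss with the sponsor.

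**Route to the primary endpoint under Reading A.** SAP Table 4 censors a patient without progression or death at the last evaluable tumor assessment. A later death, even if known, is also censored there if at least two consecutive scheduled assessments were missed first.

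**Size.** The inputs are HR 0.69, two-sided alpha 0.05, power 0.85, 262 events and 416 patients at 1:1 (Protocol 14.8, SAP 4.2).

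1. Plan's own figure, Schoenfeld formula: events = 4(1.960 + 1.036)² / (ln 0.69)² = 35.91 / 0.1377 = 260.8, so 261. Power at 262 events = Φ(√262/2 × 0.3711 − 1.960) = Φ(1.043) = 85.2%. The planned 262 is reproduced.
2. Expected events per arm = 208 × [1 − (e^(−λF) − e^(−λ(A+F))) / (λA)], with uniform accrual over A months, follow-up F and no dropout. Here λ = ln 2/8 for control and 0.69 times that for the experimental arm. With A = 15 and F = 7 (protocol), the total is 262.2. With A = 16 and F = 8 (SAP), it is 276.7.
3. Patients at risk: Protocol 11.1.2 lists PPE among Grade 3-4 reactions seen in at least 5% of cabozantinib patients. If that applies here, 0.05 × 416 = 20.8, so at least about 21 patients. This is a floor for Grade 3-4 PPE. The documents do not say what share of them would meet the stop rule, so the number affected cannot be derived.
4. Sensitivity to an assumed share of PFS events lost, as if the cutoff date were fixed:

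| Share lost (assumed) | Events | Power |
|---|---|---|
| 0% | 262 | 85.2% |
| 1% | 259.4 | 84.8% |
| 2% | 256.8 | 84.5% |
| 5% | 248.9 | 83.3% |
| 10% | 235.8 | 81.3% |

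In fact SAP 4.3 waits for about 262 events and at least 8 months after the last enrollment, whichever is later. A few lost events would therefore mainly cost time. By step 2 there may be some slack (276.7 − 262 = 14.7 events, under the design assumptions and no dropout).

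**The case against.** The strongest reply is that no site would act on the literal words. The adverse-event tables are advisory, PPE is not among the mandatory cabozantinib stops in 11.1.3.2, and the imaging rule is a protocol procedure stated several times. The protocol also uses being on study loosely for being on treatment (10.1.1, and one of the stop reasons in 11.3), so the cell may mean only that treatment ends. Stopping both drugs for a severe toxicity would not be unusual in this section, since the liver and life-threatening PE/DVT rules do so.

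Much of this stands. It makes the literal reading less likely in practice and keeps the effect small. A reader might go further the other way and infer that stopping all study treatment also contradicts 10.3, 11.1.3.2 and 11.2. The documents do not support that: the first applies when only one drug is stopped, the second is permissive and the third is conditional.

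What the reply does not do is correct the cell. Calling the table a recommendation does not tell a site that this sentence is wrong. Protocol 11.3 itself separates leaving treatment from leaving the study, so the words chosen have a meaning in this protocol, and it is the wrong one.

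**Conclusion.** The point holds as a low-severity wording conflict. Read literally, the Grade 3 PPE row contradicts the imaging and survival follow-up rules; read as stopping all treatment, it is consistent but awkward beside 10.3. The most natural explanation is a slip for cabozantinib.

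The size cannot be computed from the documents. It is likely small, because it needs a patient who meets the stop rule, has not progressed, and is treated at a site that puts this cell above the follow-up rules. The power figures above rest on assumed losses and a fixed cutoff; the real analysis is event-driven.

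Two stronger conclusions are tempting and should not be drawn. One is a ceiling on lost events: multiplying the floor of about 21 patients by a guessed share gives neither a ceiling nor an estimate. The other is a bias in favor of one arm. The protocol plans to examine whether CB-839 changes cabozantinib exposure, so equal PPE rates cannot be taken for granted, but nothing in the documents shows a difference. The reason to act is avoidable, possibly informative censoring and an unclear instruction, not power.

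**What to change.** In the Grade 3 row, keep the two triggers (recurrence after dose reduction, no improvement in six weeks) and replace the instruction they lead to with: *permanently discontinue cabozantinib, unless resumption is approved by the Medical Monitor per 11.1.3.2; CB-839/placebo should continue per 10.3 unless the investigator judges otherwise; tumor imaging and survival follow-up continue per 10.6.9, 11.3 and 10.4.*

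The word *should* matters, because it matches the direction in 10.3. Protocol 11.2 needs no change, and neither does the SAP.

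The cost is one table cell and a clarification letter to sites, a route the sponsor has already used for inclusion criterion 3e (Attachment 9).
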